A comprehensive risk analysis has been performed by AtriAN Medical Ltd in accordance with EN ISO 14971. Use of Failure Modes and Effects Analysis (FMEA) and Hazard Analysis techniques have identified potential device malfunctions and potential user errors along with clinical procedure risks. Mitigation steps to address each of the potential device malfunctions and potential user error risks along with clinical procedure risks have been implemented to reduce the risks as low as possible. These mitigation actions include extensive performance and safety testing, pre-clinical studies, development of Instructions for Use and User Manuals as well as development of user training materials. None of the remaining residual risks are higher than the risks associated with the use of currently available surgical and ablation tools. Section 8.9 of this document presents a list of the anticipated adverse events associated with GP ablation (deganglionation) in the planned concomitant open-chest surgical setting - these represent the risks associated with participation in this trial.

Of the risks directly associated with GP ablation, using the AtriAN system, that of ventricular fibrillation is noted as potentially having the highest severity. However, central to the mitigations here is the use of ECG-gated delivery of pulse energy which ensures that the ablation pulse is delivered during the refractory period of the cardiac cycle. This risk mitigation approach has been demonstrated during AtriAN's pre-clinical (animal) studies. Ventricular arrhythmia was also not observed in clinical studies that utilized voltages and pulse energies higher than AtriAN is using ^{29, 30}. Ventricular arrhythmia is not an uncommon occurrence during cardiac surgery and is dealt with using standard defibrillation techniques. Therefore, induction of ventricular fibrillation during GP ablation is not expected to harm study subjects.

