6.5 Statistical Justification and Analysis of Results

This trial is intended to demonstrate safety and feasibility and is not designed to be a statistically significant study. As a result, no formal statistical hypothesis is planned to derive the appropriate sample size.

For all primary safety and performance endpoints, the 95% 2-sided exact binomial confidence intervals will be presented.

For the secondary end-point of AERP extension, it is anticipated that a 10% extension may be obtained. This will be assessed using Paired t-testing from the pre-treatment and post-treatment AERP values from all patients.

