Rate of device related Primary Safety Adverse Events within 30 days of the procedure. Primary Safety Adverse Events include:

- 1. Atrial perforation or excessive bleeding (excessive bleeding is defined as bleeding which requires any blood transfusion).
- 2. Pericarditis
- 3. Pericardial effusion
- 4. Cardiac tamponade (if either surgical or percutaneous drainage is required).
- 5. Constrictive pericarditis, requiring re-operation.
- 6. Newly developed sinus node dysfunction.
- 7. Newly developed first, second or third degree atrioventricular (AV) block
- 8. Vasovagal reactions during hospital stay
- 9. Ventricular fibrillation

7.2 Primary Feasibility Endpoints:

The primary feasibility endpoint includes confirmation of access and delivery of Pulsed Electric Field energy to targeted ablation sites.

7.3 Efficacy Endpoints:

The clinical effectiveness endpoints are defined as the following:

- A primary efficacy end point will be confirmation of an extension in the atrial effective refractory period (AERP) through the Pulsed Electric Field ablation of the GPs. Experimental and clinical data indicates that GP ablation extends AERPs.
- A secondary efficacy endpoint will be the incidence of post-operative atrial fibrillation up to the point of patient discharge. Ablation of GPs is a potential prophylactic treatment for post-operative atrial fibrillation. Data will be collected to quantify duration (from intensive care unit (ICU) arrival) to first incidence of POAF, duration of first POAF episode and standard of care method used to treat the POAF. POAF is defined as any AF of 30 seconds or longer duration³³.

8. Study Procedure and Data Collection

The following baseline data must be collected prior to the procedure for all subjects meeting the inclusion criteria (*Assumed to be standard of care):

- Baseline:
 - Inclusion/Exclusion criteria
 - Signed Informed Consent
 - Frequency of reported episodes of atrial fibrillation *
 - Medical History including NYHA class *
 - Documentation of Smoking and Substance abuse *
 - Medication History, review of current and past Medications*
 - General Physical Exam*
 - 12 Lead ECG*
 - 24Hr Holter recording documentation of AF, frequency and severity of AF and presence of asymptomatic episodes if relevant
 - TTE for LVEF and LA diameter*
 - Blood sample for laboratory investigation comprising Hgb, WBC, Platelet, Na, K, Creatinine, NTproBnP, Troponin, C-reactive protein, TSH, INR *
 - Short form-36 (SF-36) QOL

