8.9 Anticipated Adverse Events

The following adverse events have been identified for the atrial deganglionation and for the open-chest cardiac surgery.

Note: Arrhythmia events are not uncommon during cardiac surgery procedures and will not be identified as adverse events if AE/SAE definitions per section 8.8 are not met.

Study-specific SAEs that may be directly related to atrial deganglionation:			
Note:	Note: Each event must first meet the SAE definition as described in section 8.8 to be defined a		
	SAE.		
1.	Emergency during the procedure requiring change in surgical strategy		
2.	Atrial perforation or excessive bleeding (excessive bleeding is defined as bleeding which requires any blood transfusion).		
3.	Hemothorax or pleural effusion		

DESCRIPTION: CIP-001 Clinical Investigation Plan for OCED System

Atri

1.	Pericarditis
5.	Pericardial effusion
6.	Cardiac tamponade (if either surgical or percutaneous drainage is required).
7.	Constrictive pericarditis, requiring re-operation.
8.	Documented atrial or ventricular arrhythmia during hospital stay
9.	Newly developed sinus node dysfunction.
10.	Newly developed first, second or third degree AV block
11.	Persistent chest pain
12.	Phrenic nerve damage
13.	Hypotension
14.	Prolonged Hospitalization
15.	Vasovagal reactions during hospital stay
16.	Perforation of great vessels
17.	Perforation of lung
18.	Perforation of esophagus
19.	Myocardial damage
20.	Burns
21.	Ventricular fibrillation
22.	Coronary sinus damage
23.	Pulmonary vein stenosis
24.	Infection

Note:	Each event must first meet the SAE definition as described in section 8.8 to be defined as an SAE.		
1.	Death (within the first 30 days post-operative or > 30 days if procedure related		
2.	Cardiac or respiratory arrest/depression during hospital stay		
3.	Stroke (resulting in neurological deficit lasting more than 24 hours or lasting 24 hours or less		
	with a brain imaging study showing infarction).		
4.	Transient Ischemic Attack (TIA) or a neurological deficit lasting less than 24 hours, and if an		
	imaging study is performed showing no evidence of infarction.		
5.	Myocardial infarction (according to ESC Guidelines definition)		
6.	Documented atrial or ventricular arrhythmia during hospital stay		
7.	Congestive heart failure, including volume overload		
8.	Prolonged Hospitalization		
9.	Coronary artery dissection, spasm or occlusion		
10.	Perforation of the lung		
11.	Hemothorax or pleural effusion		
12.	Pneumothorax		

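### The 30-day primary safety rate has nine listed components and no catch-all, so a device-related death or other serious device effect counts only if a listed event accompanies it

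*Combined protocol and SAP*

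**What the plan says.** The primary safety endpoint in Section 7.1, repeated in the synopsis, reads "Rate of device related Primary Safety Adverse Events within 30 days of the procedure. Primary Safety Adverse Events include". Nine numbered entries follow, ending with "9. Ventricular fibrillation". No entry covers other device-related serious events, and no seriousness threshold is set.

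Section 8.9 has two lists. The first is headed "Study-specific SAEs that may be directly related to atrial deganglionation" and has 24 entries, among them "Phrenic nerve damage" and "Perforation of esophagus". Each must meet the SAE definition of Section 8.8 before it is classed as an SAE. The second list, for the open-chest surgery, begins with "Death (within the first 30 days post-operative or > 30 days if procedure related". Section 5 says of the Section 8.9 events that "these represent the risks associated with participation in this trial".

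Section 6.5 states the analysis: "For all primary safety and performance endpoints, the 95% 2-sided exact binomial confidence intervals will be presented". The synopsis adds that the study is unpowered and descriptive. Section 7 has no secondary safety endpoint.

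**The concern.** The endpoint is a subset of the protocol's own list of possible device harms, and no section explains how the subset was chosen. Some of the harms left out are ones on which the case for the technology rests. Section 1 supports the safety of pulsed-field ablation by the absence of oesophageal and phrenic nerve injury in early reports, and Section 6.1 builds minimal myocardial ablation into the primary hypothesis. Yet phrenic nerve damage, oesophageal perforation and myocardial damage are not components.

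The threshold is also uneven. A device-related first-degree AV block or any device-related pericardial effusion counts even if it is not serious, while a device-related oesophageal perforation without a listed event does not.

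This is a first-in-human safety study, and the 30-day rate is the safety result that will be quoted. It could be 0% although a patient had a serious device effect. The error would be in the favourable direction.

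**Working it through.** **Step 1: compare the lists.** Section 7.1 has 9 entries and the deganglionation list in Section 8.9 has 24. In printed order, the nine endpoint events match entries 2, 4, 5, 6, 7, 9, 10, 15 and 21. That leaves 24 − 9 = 15 not named:

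- 1 emergency change of surgical strategy
- 3 haemothorax or pleural effusion
- 8 atrial or ventricular arrhythmia in hospital
- 11 persistent chest pain
- 12 phrenic nerve damage
- 13 hypotension
- 14 prolonged hospitalisation
- 16, 17, 18 perforation of great vessels, lung, oesophagus
- 19 myocardial damage
- 20 burns
- 22 coronary sinus damage
- 23 pulmonary vein stenosis
- 24 infection

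Entry 8 partly overlaps with ventricular fibrillation, which is in the endpoint. So 14 are wholly outside and 1 partly. Death is on the surgical list only and is not among the nine.

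**Step 2: effect on the reported rate.** The plan states no expected rate, margin or performance goal, so there is no figure to reproduce. As an illustration, suppose one patient has an omitted device-related event and no patient has a listed one. Inputs: up to 30 treated patients (Section 6.4) and two-sided 95% exact intervals (Section 6.5).

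- For 0 of n, the upper limit is 1 − 0.025^(1/n). At n = 30: 1 − 0.025^(1/30) = 11.6%.
- For 1 of n, the lower limit is 1 − 0.975^(1/n), which is 0.1% at n = 30. The upper limit p solves (1 − p)^30 + 30p(1 − p)^29 = 0.025, giving 17.2%.

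| n | Nine-event list | With the event counted |
|---|---|---|
| 30 | 0/30 = 0% (0 to 11.6%) | 1/30 = 3.3% (0.1 to 17.2%) |
| 20 | 0/20 = 0% (0 to 16.8%) | 1/20 = 5.0% (0.1 to 24.9%) |
| 10 | 0/10 = 0% (0 to 30.8%) | 1/10 = 10% (0.3 to 44.5%) |

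**Step 3: how likely is it to matter?** The documents give no risk for the omitted events. If their combined per-patient risk is assumed to be p, the chance of at least one in 30 patients is 1 − (1 − p)^30: 26% at p = 1%, 45% at 2%, 79% at 5%. These are assumptions to show the range. They also overstate the effect to the extent that an omitted event is accompanied by a listed one.

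**The case against.** A focused endpoint drawn from a broader list of anticipated events is not in itself a contradiction, and the two lists serve different purposes. Several stronger readings are tempting, and the documents do not support them.

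- *The gravest events are left out.* Section 5 names ventricular fibrillation as potentially the most severe risk directly associated with the ablation, and it is in the endpoint. So are atrial perforation, tamponade needing drainage, constrictive pericarditis needing re-operation and third-degree AV block.
- *A device-related death or perforation always scores zero.* The first component includes bleeding that needs any transfusion, so a perforation with transfused bleeding would count. So would a patient who died through device-related tamponade or ventricular fibrillation.
- *63% of the device risk is missing.* The fraction 15/24 counts entries, not risk. The 15 include hypotension, chest pain, infection and prolonged hospitalisation, which are non-specific after bypass surgery.
- *Serious device effects would go unseen.* Section 8.8 requires reporting of serious events to the sponsor within 24 hours, to authorities within 2 or 7 days, and to all principal investigators. The Clinical Events Committee (Section 13.9) reviews events in question and may recommend termination.
- *The list is closed beyond doubt.* The text says that the events include these nine. A numbered list, repeated identically and without a residual item, is most naturally read as closed. If it were open, the endpoint would be undefined, and the same wording change would be needed.

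It is also fair that no stated decision rule depends on the rate. What remains is that nothing in the plan brings a device-related death or other unlisted serious device effect into the headline figure, and no reason for the subset is given.

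**Conclusion.** The point holds as a gap in the definition of the primary safety rate. The counts (9 listed, 24 anticipated, 15 not named, of which 14 wholly outside) are exact, and the absence of device-related death as a component is plain. The consequence is conditional: the rate is too low only when an omitted event occurs without a listed one. In that case, at the maximum of 30 patients, a single event moves the result from 0% (0 to 11.6%) to 3.3% (0.1 to 17.2%), and the shift is larger with fewer patients. The conclusion assumes that the nine-event list is closed. The rate would be incomplete; the underlying safety data would not be. Because the remedy is cheap and the safety rate is the main product of a first-in-human study, the change should be made.

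**What to change.** In Section 7.1 and the synopsis, add a tenth component: *device-related death or any other serious adverse device effect (SADE) within 30 days*. Count the composite per patient, which the exact binomial interval requires, and report it with its 95% interval. Tabulate each component, and show the current nine-event rate alongside so that both can be read.

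Keep the attribution as device related. Importing every Section 8.9 entry, or widening attribution to the ablation procedure, is debatable and not needed: the SADE criterion already admits an entry when it is both serious and device related.

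The cost is wording only, because Section 8.8 already requires all adverse events to be recorded with relatedness. The downside is a possibly slightly less favourable rate. The change does not improve detection: the schedule in Section 8.4 has no imaging after the procedure, so a silent injury such as pulmonary vein stenosis could still be missed.

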8.1 Informed Consent

Patients will be asked to sign informed consent after an explanation of the risks and potential benefits has been provided. Informed consent must be obtained from each patient prior to conducting any study-related procedures including screening procedures that are not part of the standard of care at the institution. Patients with a planned cardiothoracic surgical procedure will receive written information about the study prior to their scheduled procedure date to give sufficient time to carefully read the patient information letter. During the pre-procedural outpatient clinic visit the investigator or his staff will provide information about the study in case any questions remain. The information is intended to give each participant a thorough understanding of the purpose and the nature of the trial, the cooperation required, anticipated benefits, and potential hazards of the study and that if he/she does so then he/she receives standard treatment with the same degree of care. It is the responsibility of the treating physician or his staff to obtain written informed consent (according to local legal requirements and regulations). A consent

form (in the native language) will be made available. The consent form will be signed and dated by both the investigator or his staff and the subject. The subject is obliged to date the informed consent him/herself. The fact that informed consent was obtained is recorded in the Case Report Form (CRF). Screening failures will not be followed further and will not be counted toward the maximum possible

patients who receive treatment.

The Investigator will retain an original of the signed informed consent document in each patient's record, and also provide an original to the patient. The Investigator shall not request the written informed consent of any patient and shall not allow any patient to participate in the investigation, before obtaining Ethics Committee (EC) and or Competent Authority approval.

Prior to starting the study, the Investigator will provide the Sponsor with a copy of the Informed Consent Document approved by the EC with documented evidence that the EC has approved the protocol.

8.2 EDC Data Collection Platform

Study data will be recorded in a limited-access, secure electronic data capture (EDC) system with data entry into electronic case report forms (eCRFs) that capture the data for each enrolled Subject, as required by the clinical study protocol. Data reported on the CRF, which are derived from Source Documents, must be consistent with the Source Documents or the discrepancies must be explained.

Investigators are responsible for ensuring the accuracy, completeness, legibility, and timeliness of the data reported to the Sponsor in the eCRF. eCRFs must be completed by Investigators or their authorized personnel.

An audit trail must be maintained for any changes or corrections to an eCRF.

Paper CRF changes or corrections must be dated, initialled, and explained (if necessary) and must not obscure the original entry. Changes and corrections to eCRFs should be made by the data originator, Investigator or their authorized personnel. If it is necessary for Sponsor personnel to make changes to the eCRF, a justification for the necessity should be documented and any such changes must be endorsed by the Investigator.

By default, users of the EDC system should have view-only permissions, unless the user's specific role requires entering or changing data. A list of all individuals with authorized access the EDC will be maintained. The list of authorized users will reflect the permissions assigned for each user and the dates that access was granted and terminated. Access will be terminated as soon as possible for users that are no longer working on the study (e.g., terminated employees, site closures, Investigator disqualification, etc.) and for users that have demonstrated intentional misuse.

The EDC system will be designed with computer-generated, time-stamped electronic audit trails. Audit trails must apply to the creation, modification or deletion of any data elements and must capture the user that is creating, modifying or deleting data. The reason for modifications and deletion of data should also be captured.

Data will be backed up and archived in a manner that protects against catastrophic loss and ensures the quality and integrity of the data.

Signed electronic records must contain the following information associated with the signing that clearly indicates:

- Printed name of the signer;
- Date and time when the signature is executed; and
- Meaning (such as review, approval, responsibility or authorship) associated with the signature.

An electronic signature must be linked to the respective electronic record to ensure that signatures cannot be excised, copied, or otherwise transferred to falsify and electronic record by ordinary means. Each

electronic signature must be unique to one individual and may not be reused or reassigned to anyone else.

The system facilitating electronic signatures will be designed so that the attempted use of an electronic signature by anyone other than the genuine user requires collaboration by two or more individuals.

8.3 Study Completion

The date of study completion for study subjects who complete all follow-ups is recorded on the STUDY COMPLETION Case Report Form.

8.4 Schedule of Events

The tests and measurements to be conducted at baseline, during the treatment procedure, and during follow-up visits are illustrated in the following chart. (*Considered as Standard of Care)

Schedule of Tests:	Baseline	Procedure	Post- Procedure to Discharge	Discharge	30 Days ±7 days	3 Mo ±30 Days	6 Mo ±45 Days	12 Mo ±60 Days
Subject Eligibility/ Informed Consent	x							
Medical history & Demographics*	x							
NYHA Score*	х							х
Physical Exam*	х			х	х	Х	Х	х
TTE for LVEF and LA diameter*	x							
Blood tests*	х						Х	
SF-36 QOL	х							х
Medication Log (AAD-ATT)*	х			х	х	Х	Х	х
ECG (12 Lead) *	х			х	Х	Х	Х	х
TEE to exclude thrombus*	х							
24HR Holter *	х				х	Х	Х	х
Cardiac Telemetry			Х					
Adverse Events	х	х	х	Х	Х	Х	Х	х
Protocol Deviation	х	х	х	Х	Х	Х	Х	х
Device Performance		х						
AERP		х						

NYHA – New York Heart Association; TTE – transthoracic echocardiography; LVEF – left ventricular ejection fraction; LA – left atrium; SF-36 – Short Form 36; AAD-ATT – antiarrhythmic drugs and antithrombotic therapy; ECG – electrocardiogram; TEE – transesophageal echocardiography; AERP – atrial effective refractory period.

8.5 Patient Lost to Follow-Up

The investigator will attempt to contact a subject at least three times prior to designating them as lost-tofollow-up subjects; two of these attempts should include attempting to contact subject via registered mail. The investigator will document the date and type of attempted communication and will complete the STUDY COMPLETION Form when a patient is lost to follow-up.

8.6 Patient Withdrawals and Discontinuation

Subjects have the right to withdraw from the clinical investigation at any time and for any reason without prejudice to their future medical care by the investigation team or investigation site. The investigator will ask for the reason for their withdrawal and will record all information regarding the patient

discontinuation on the STUDY EXIT Case Report Form. An investigator may also withdraw a patient from study participation at any time and shall report the reason for withdrawal to the Sponsor.

A subject may be withdrawn from the clinical investigation for the following reasons:

- Subjects may choose to withdraw from the clinical investigation under the terms of the Declaration of Helsinki and their consent documentation without having to give a reason;
- Any unanticipated adverse reaction which is, in the opinion of the Investigator, related to the treatment and will endanger the well-being of the patient if treatment is continued;
- Development of any intercurrent illness(es), infection or condition(s) that might interfere with the Clinical Investigational Plan;
- Non-compliance with the clinical investigation procedures deemed by the Investigator to be sufficient to cause discontinuation;
- Any problem deemed by the Investigator to be sufficient to cause discontinuation.

Investigator will treat all subjects discontinued from the investigation due to an unanticipated adverse reaction, directly related to the investigation, until the reaction resolves.

Investigator will not replace subjects who have withdrawn from the clinical investigation if they were treated with the investigational device. If possible, Investigator will perform any procedures or assessments planned for the subject at the time of withdrawal.

If the decision to terminate the study is made by the sponsor or the study doctor, the Ethics Committee that approved the study must be notified immediately and will evaluate the reasons for the termination of the study. In urgent cases, the study will be terminated to ensure study participant safety, and the Ethics Committee will be notified as soon as possible.

